9.6.1 Study Monitoring Committee

The study will be monitored intensely by the protocol team, which will review safety and pharmacokinetic data approximately monthly. In addition, the study will be monitored by an SMC according to standard IMPAACT procedures. The committee will meet via conference call to review relevant data as described below and in Section 7.1 to ensure participant safety. The SMC could meet at least once annually and more frequently if indicated by the protocol team or the study sponsor.

9.6.2 Study Safety Monitoring

Since Phase I studies are not routinely reviewed by a Data and Safety Monitoring Board (DSMB), it is the responsibility of the Protocol Team to interpret safety data and make decisions regarding AEs that are needed to protect participants from undue risk. Per Section 7.1, the Core Team will review routine safety monitoring and clinical data reports. In addition, the Study Monitoring Committee described above is appointed to provide impartial reviews in situations where participant safety is in question.

The safety and tolerability of the study agent will be monitored by means of adverse events reports and toxicity reports presenting laboratory and clinical events. The data required for the toxicity reports must be entered into the database within 48 hours of the time at which the results of the laboratory tests or clinical examinations become available.

Reports compiled by the DMC will be reviewed and discussed by the Protocol Team on conference calls held approximately monthly. The attribution of relationship of \geq Grade 3 AEs to RPT/INH will be determined by the protocol team, and any discrepancies of assessments between site investigators and the protocol team will be reconciled during the conference calls. For safety monitoring, a drug-related AE is an AE that is judged to be definitely, probably, or possibly related to study drug (RPT/INH).

Data on accrual, pharmacokinetics and toxicity will be reviewed by the study's Study Monitoring Committee:

- 1) When the consensus among the site investigator, the protocol team and the DAIDS medical officers regarding to relationship of AEs to the study drug cannot be established
- 2) When there is any specific safety concern.

Adverse events will be monitored from screening onward throughout the follow-up period. If any Grade 4 AEs that are possibly, probably, or definitely related to the study regimen or deaths occur, or if the protocol team identifies any potentially treatment-related toxicities that could compromise participant safety, the study may be paused, and the Study Monitoring Committee will review all relevant data and will determine whether, and under what conditions, the study will be allowed to proceed.

9.7 Analysis

9.7.1 Pharmacokinetic Outcomes

Analysis for objectives 2.1.1, 2.2.1, 2.2.2, 2.2.3, 2.2.4, 2.2.5, 2.2.8, and 2.3.1 is fully described in Section 10 below.

9.7.2 Safety Outcomes

The primary safety analysis will include all women who have been exposed to RPT/INH at any dose in the study. Women whose doses have been adjusted for inadequate PK will be included in the primary safety analysis. Women who have been removed from treatment due to toxicities while on the optimal dose will be included and treated as safety failures in the primary safety analysis. Additional analyses will look at the combined data from women whose doses failed and those who have been treated solely at the optimal doses determined for their cohorts. Each woman's safety data will be summarized as: the worst grade of adverse event experienced during study treatment and the worst grade of adverse event judged to be at least possibly related to study treatment during this time period.

Frequency distributions of these safety outcomes will be presented in the aggregate and broken down by cohort. Listings of all \geq Grade 3 or ICH defined serious events will be provided. The proportions of participants experiencing \geq Grade 3 or ICH defined serious adverse events will be presented in aggregate and broken down by cohort, with these proportions bounded by exact 95% confidence intervals. Similar analyses will present the proportions of participants exhibiting \geq Grade 3 or ICH defined serious events which have been judged to be at least possibly related to study medication, again bounded by exact 95% confidence intervals.

For objectives 2.1.2, 2.1.3, and 2.2.6, Poisson regression will be used to estimate the incidence of serious adverse events related to treatment, adjusting for important cofactors. Analyses of tolerability and safety for infants will employ standard descriptive techniques; events of intolerability or compromise to infant safety are expected to be rare.

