10.5 Primary and Secondary Data Analysis Plan

Primary: Pharmacokinetic data (concentration-time data) and safety data of rifapentine and desacetyl-rifapentine in pregnant women; safety outcomes in infants

Secondary: Pharmacokinetic data of rifapentine and desacetyl-rifapentine in postpartum women and infants; pharmacokinetic data of isoniazid in pregnant and postpartum women

Population-based estimates of RPT CL/F, absorption, and volume of distribution will be derived for pregnant women in second and third trimesters of pregnancy and in the postpartum period. Study data will provide a mix of longitudinal and cross-sectional observations, which will be combined using standard algorithms in wide use in pharmacology research. The pharmacokinetics of the desacetyl-rifapentine (des-RPT) metabolite of RPT and INH will be estimated based on the sample in like fashion. Rates of adverse events and other safety-related parameters will be computed and reported for study monitoring and regulatory use. Secondary objectives are: characterization of PK data of RPT and des-RPT in the postpartum period, description of adverse and safety outcomes in pregnant women, assessment of impact of covariates on primary PK parameters, comparison of RPT and des-RPT exposures between study participants and non-pregnant historical controls, estimation of effective RPT dose for pregnant women, estimation of RPT concentrations in newborns, description of pregnancy and infant safety outcomes, description of RPT + INH tolerability in pregnancy, and characterization of PK data of INH in pregnant and postpartum women.

The primary tool for estimation of parameters of interest is the single compartment model for RPT absorption and disposition kinetics:

$$\frac{dA(1)}{dt} = -ka \times A(1); \text{ Absorption compartment}$$
$$\frac{dA(2)}{dt} = ka \times A(1) - \frac{CL}{V} \times A(2); \text{ Central Plasma compartment}$$

The parameters CL and V will be elaborated upon to incorporate allometric scaling and effects of gestational age.

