10.6 Anticipated Outcomes

The anticipated outcomes of the pharmacology evaluations are:

- Estimates of all PK parameters including CL (in relationship to the pregnancy stage), volume of distribution, model-based C_{max} and exposure (AUC) as well as estimates between participant variability associated with all these parameters.
- Absorption rate constant (ka) of RPT.
- Incidence of adverse safety events in pregnant women and their infants.

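### Section 9.7.2 gives non-serious Grade 1-2 maternal events an on-treatment table only, and assigns related-SAE incidence to a covariate-adjusted Poisson regression with no fallback for few or no events

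*Protocol*

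**What the plan says.** **Lower-grade events.** Protocol Section 9.7.2 reduces each woman's safety data to "the worst grade of adverse event experienced during study treatment" and the worst related grade over the same period. These are tabulated overall and by cohort. Every other listing or proportion in the section concerns events of Grade 3 or higher, or serious events, and states no time window.

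**Outcomes and data collection.** Section 9.2.1.2 makes related Grade 2 events a primary maternal safety outcome without an on-treatment limit, and the introduction to Section 9.2 includes the postpartum period. Section 9.6.2 says: "Adverse events will be monitored from screening onward throughout the follow-up period". Section 7.2 keeps recording Grade 2 or higher pregnancy complications, hepatotoxicity, hemorrhage and neuropathy after study drug ends.

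**Related SAEs.** For objectives 2.1.2, 2.1.3 and 2.2.6, Section 9.7.2 says that "Poisson regression will be used to estimate the incidence of serious adverse events related to treatment, adjusting for important cofactors". The paragraph before gives proportions of women with Grade 3 or higher or serious events "judged to be at least possibly related to study medication, again bounded by exact 95% confidence intervals".

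**Infants.** Objective 2.1.3 is assigned to the regression, but the next sentence reads: "Analyses of tolerability and safety for infants will employ standard descriptive techniques".

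**Elsewhere.** Section 10.5 adds that "Rates of adverse events and other safety-related parameters will be computed and reported for study monitoring and regulatory use", and Section 10.6 lists "Incidence of adverse safety events in pregnant women and their infants". Neither gives a grade, window or table. The SAP names safety data in its primary objective but specifies only pharmacokinetic methods.

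**The concern.** Maternal and infant safety are primary objectives, and two stated analyses do not fit what they are meant to report.

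First, outcome and summary do not match. A non-serious Grade 2 event at delivery or postpartum, in a woman who has finished the regimen, is collected and may belong to a primary outcome, but it has no specified table. Section 8.2 itself separates being on study from being on treatment, so the on-treatment wording cannot easily be read as all of follow-up.

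Second, the trial hypothesises no SAEs, yet the method named for their incidence is a regression that yields no usable log-scale estimate or Wald interval in that case. The primary related-SAE result could then depend on an analysis chosen after the data are seen.

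**Working it through.** **1. The plan's own figures reproduce.** Section 9.5.2 gives 90% power to see at least one event with 50 women and a 5% rate. Poisson: 1 - exp(-2.5) = 91.8%; binomial: 1 - 0.95^50 = 92.3%. Its upper bounds of about 15% (0/25) and 30% (2/25) match exact Poisson limits of 14.8% and 28.9%. All 12 cells of Table 4 reproduce under a Poisson model.

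**2. When treatment ends relative to delivery.** Dose 1 is at entry, so with weekly dosing dose 12 falls 11 weeks later.
- Cohort 1 (entry 14 to <28 weeks): 14 + 11 = 25 to <28 + 11 = 39 weeks. A 40-week delivery follows dose 12 at every entry age.
- If dosing takes the full 16 weeks (Section 5.1.2), this holds for entry before 24 weeks.
- For a 37-week delivery it holds for entry before 26 weeks (weekly dosing) or 21 weeks (16-week dosing).

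**3. Share of maternal follow-up on treatment.** Share = T / [(D - entry) + 24], with T = 11-16 weeks and delivery at D = 37-40 weeks (an assumption).

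| Entry (weeks) | D | T | Share |
|---|---|---|---|
| 14 | 40 | 11 | 11/50 = 22% |
| 14 | 37 | 16 | 16/47 = 34% |
| 28 | 40 | 11 | 11/36 = 31% |
| 34 | 40 | 16 | 16/30 = 53% |
| 34 | 37 | 16 | 16/27 = 59% |

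**4. Chance of zero related SAEs**, (1 - p)^n, for 50 evaluable women and the maximum of 82 (Section 9.4).

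| Assumed true rate | n = 50 | n = 82 |
|---|---|---|
| 1% | 61% | 44% |
| 5% | 8% | 1.5% |
| 10% | 0.5% | 0.02% |

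The documents give no related-SAE rate. For orientation, Section 1.2 reports 0.4% drug-related hepatotoxicity and 0.37% severe hypersensitivity with this regimen (0.77% together if they do not overlap; these are not SAE rates). Table 4 uses 5-15% for safety events in general.

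**5. Behaviour of the model.** With all counts zero, the likelihood rises as the log rate goes to minus infinity, so there is no finite estimate and no Wald interval; a Poisson fit to 0/50 failed. With 2/25 against 0/25 and a cohort term, the fitted coefficient was -20.4 with a standard error of about 11,000, which marks a non-finite estimate. The second case arises only if cohort is a model term, which the plan does not say.

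**6. What the planned exact intervals give.** Two-sided 95% Clopper-Pearson upper bounds:
- No events, 1 - 0.025^(1/n): 13.7% (0/25), 7.1% (0/50), 4.4% (0/82).
- Grade 3 or higher and serious events read as one composite, with no related SAE among 50 women: 10.6% if one woman has a non-serious related Grade 3 or higher event, 21.8% if five do, against 7.1% for related SAEs alone. The counts of one and five are illustrations.

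**The case against.** **On the window.** An on-treatment worst-grade table is a reasonable summary. Rifapentine's half-life is 11-18 hours (Section 1.2), so events weeks after the last dose are hard to attribute to drug. The related Grade 2 outcome is not itself truncated; what is missing is a table for it. This stands, and it is why the on-treatment table should be kept alongside a longer one. A reader might infer that severe or serious postpartum events are lost. The documents do not support that: those analyses state no window, and a lower-grade event that is serious enters them.

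**On the model.** A reader might infer that the regression is the only analysis bearing on related SAEs. It is not. The preceding paragraph plans exact intervals, and listings, for Grade 3 or higher or serious events. If those two categories are tabulated separately, related SAEs are covered directly. If they form a composite and it has no events, the bound for related SAEs is the same. Only a non-empty composite leaves related SAEs loosely bounded. Section 9.5.2 also shows that the zero-event case was considered at design.

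A reader might also infer that Poisson methods cannot handle zero events at all. They can: the rate estimate is 0, and an unadjusted profile-likelihood 95% upper limit is finite (1.92/50 = 3.8%; 1.92/82 = 2.3%). The failure lies in log-scale maximum-likelihood and Wald output. Nor does a non-finite cohort coefficient by itself prevent an overall incidence estimate.

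**On the source.** The SAP is a pharmacokinetic plan. A separate safety plan may settle these points, but none is supplied.

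**Conclusion.** The point holds in a limited form. In the documents supplied, non-serious Grade 1-2 maternal events have a specified summary only for the treatment period. That period is about 22-59% of follow-up from entry, given 11-16 weeks of dosing and delivery at 37-40 weeks. With weekly dosing, a Cohort 1 woman delivering at 40 weeks has always finished treatment. The general statements in Sections 10.5 and 10.6 do not fill the gap. The documents give no rate for non-serious Grade 2 delivery and postpartum events, so the number affected cannot be calculated.

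For related SAEs as a stand-alone primary quantity, the named regression has unnamed cofactors and no sparse-event fallback. With 50 women the zero-event problem is likely at a true rate near 1%, modest at 5% and small at 10%; these rates are assumptions. The planned exact intervals soften it but do not estimate related SAEs separately unless the categories are tabulated apart, which the plan does not say. Nothing is irrecoverable, because the data are collected and serious events are listed. The change should be made; confidence is moderate because a safety analysis plan may exist that cannot be seen here.

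**What to change.** 1. Present worst grade, any-cause and related, both on treatment and from first dose to study exit. State the window for every safety table.
2. Make the exact 95% interval for related SAEs alone the primary estimate for objective 2.1.2 (binomial for the proportion, or Poisson for the rate), overall and by cohort.
3. Keep the Poisson regression as exploratory, run only if events allow, with its cofactors named in advance.
4. For infants, where the section names both approaches, use descriptive summaries with exact intervals.
5. If a separate safety analysis plan already covers these points, cite it in Section 9.7.2.

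Cost: a few sentences of plan text and a few more tables from data already collected. The longer window adds background events unrelated to drug, which is the reason for showing both windows.

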10 CLINICAL PHARMACOLOGY PLAN

10.1 Pharmacology Overview and Objectives

The goal of this study is to assess the pharmacokinetics of RPT, des-RPT, and INH in pregnant women. Population pharmacokinetics will be estimated based on the sample, and exposure parameters will also be compared between the pregnant cohort and non-pregnant historical controls (58). Finally, this study will determine how stage of pregnancy impacts the pharmacokinetics of RPT and des-RPT and dosing.

The design and analysis plans for objectives 2.1.1, 2.2.1, 2.2.2, 2.2.3, 2.2.4, 2.2.5, 2.2.8, and 2.3.1 are described in this section.

10.2 Methods and Timing for PK Collections, Processing, Handling, and Storage

10.2.1 Intensive and Sparse PK collections: Mother

Both the Intensive and Sparse PK sampling are ideally conducted in the morning. The Intensive PK sampling must be initiated on the same day as the first dose of the study drug regimen per Section 6.2. As mentioned in Section 6.2 above, the Entry Visit may be conducted as a split visit. The Sparse PK sampling will be completed after the final study drug dose per Section 6.3. Depending on site capacity, women may stay at the clinical research site or affiliated health care facility the evening prior to and after the PK sampling dose in order for an early morning PK sampling to be initiated. Further operational details on these visits are found in Sections 6.2 and 6.3.

10.2.2 Breast Milk PK Collection: Mothers

Postpartum women who are breastfeeding while still on the study drug regimen will be eligible for the breast milk PK sample collection. Breast milk will be expressed by the woman, and a plasma sample collection will also be drawn per Section 6.3.

10.2.3 Cord Blood PK Collection: Mothers

At sites with capacity, women will be offered an option of also having a cord blood sample taken. Women must have received a study drug regimen dose within 72 hours prior to delivery to be eligible for the cord blood sample collection.

10.2.4 Single PK collection: Infant

For infants meeting PK sampling eligibility criteria described below, a single PK sample will be obtained within the first three days of life. Ideally, the single PK sample for the infants will be obtained prior to the mother being discharged from the hospital.

Infants must meet all of the criteria below to be eligible for the Infant PK Sample Collection:

- Infant birth weight > 1000 grams
- Infant NOT receiving disallowed medications described in Section 5.5
- Infant does not have any severe congenital malformation or other medical condition not compatible with life or that would interfere with study participation or interpretation, as judged by the site investigator
- The mother's most recent dose was taken within 72 hours of drawing the infant's blood

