2.2 Secondary Objectives

- 2.2.1 To estimate the population pharmacokinetics (PK) (CL/F, absorption, volume of distribution) of RPT and its desacetyl-rifapentine metabolite (desRPT) among pregnant women during the postpartum period who are receiving once-weekly RPT (900mg or the new study dose, if a dose adjustment is indicated by the interim analysis) and once-weekly INH (900mg).
- 2.2.2 To assess the impact of covariates (gestational age, weight, age, HIV status) on primary PK parameters using population PK modeling.
- 2.2.3 To compare RPT and desRPT exposure pharmacokinetic parameters (AUC, C_{max} , C_{min}) for RPT in pregnant and postpartum women versus non-pregnant historical controls, using noncompartmental analyses.
- 2.2.4 To determine the RPT dose in pregnancy that achieves similar estimated exposure (AUC) of RPT as non-pregnant adults at standard doses.

- 2.2.5 To quantify RPT and desRPT concentrations at delivery among infants born to women receiving once-weekly RPT + INH.
- 2.2.6 To describe the tolerability of RPT + INH dosed once weekly for 12 weeks in pregnant and postpartum women.
- 2.2.7 To assess incidence of active TB in mother-infant pairs up to 24 weeks postpartum.
- 2.2.8 To explore the population pharmacokinetics (PK) (CL/F, absorption, volume of distribution) of INH in HIV-1-infected and HIV-1-uninfected pregnant and postpartum women (i.e., women who are and are not taking efavirenz (EFV)) who are receiving once-weekly RPT (900mg or the new study dose, if a dose adjustment is indicated by the interim analysis) and once-weekly INH (900mg).

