3 STUDY DESIGN

3.1 Identification of Study Design

IMPAACT 2001 is an open-label, multi-center, intensive PK study to evaluate the pharmacokinetics, safety, and tolerability of RPT and INH dosed once weekly for 12 doses in HIV-1-infected and HIV-1-uninfected pregnant women with latent TB infection at high risk for development of TB. Infants will also be enrolled, and breast milk samples from postpartum women who are still taking RPT/INH will be collected.

Each enrolled woman will receive the study drug regimen and will be followed for 24 weeks postpartum, regardless of when she delivers. Therefore, it is expected that some women will continue the study drug regimen postpartum, while some women may have completed the study drug regimen prior to delivery. It is possible that a woman enrolled in Cohort 1 could continue the study drug regimen postpartum (e.g., if she delivers her infant pre-term).

Two study cohorts are planned:

- Cohort 1: Pregnant women ≥ 14 weeks gestation through < 28 weeks gestation (second trimester)
- Cohort 2: Pregnant women ≥ 28 weeks gestation through ≤ 34 weeks gestation (third trimester)

An interim analysis to assess the PK of RPT will be conducted, and a dose adjustment may be indicated for each cohort (see Section 10). Dose adjustments indicated for Cohort 2 will be implemented for Cohort 1 women as they enter their third trimester of pregnancy. See Section 3.4 for accrual into the cohorts, and Section 10.3 (Interim Analysis and Dose Adjustment) for further details regarding the interim analysis and dose adjustment.

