6.5 Infant/Newborn Visit

The infant single PK sample collection will be conducted within three days of life, ideally in the morning. When a study participant is admitted for delivery, the research team should be notified (i.e., the medical records may indicate that the patient is enrolled in IMPAACT 2001, and the research staff's contact information may be available). The participants may also be asked to contact the research staff once they are in labor. The infant single PK sample will only be collected if the mother's most recent dose was taken within 72 hours of drawing the infant's blood.

At sites with capacity, cord blood PK sample collection will be offered to mothers to be conducted during labor and delivery. See Section 10 below for details and eligibility of the single PK sample and cord blood sample collections. Eligibility for single PK sampling must be confirmed prior to collection of this sample.

Infant/Newborn Visit Procedures (within 3 days of life)	
Administrative and Regulatory	
 • None
Clinical	
 • Assess eligibility for single PK sampling • Complete physical exam • Record medical and medications history • Record AEs • Provide available test results to mother
Laboratory	Collect blood for: 
 • Single PK sample collection (if eligible) • Coagulation profile (if eligible) • Cord blood (optional if eligible, during mother's delivery)

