9.2.2 Secondary Outcome Measures

9.2.2.1 Vd, CL/F, Ka for pregnant women in their second or third trimester.

9.2.2.2 RPT and desRPT concentrations in infants born to women receiving once-weekly RPT + INH.

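### Infant PK eligibility is tied to the mother's last dose before the blood draw, not before birth, so some samples may not describe concentrations at delivery

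*Protocol*

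**What the plan says.** - Protocol 2.2, objective 2.2.5: "To quantify RPT and desRPT concentrations at delivery among infants born to women receiving once-weekly RPT + INH".
- Protocol 6.5: "The infant single PK sample will only be collected if the mother's most recent dose was taken within 72 hours of drawing the infant's blood". Section 10.2.4 repeats the criterion, "The mother's most recent dose was taken within 72 hours of drawing the infant's blood", and sets the window: "a single PK sample will be obtained within the first three days of life". Neither section says that the dose must come before birth.
- Protocol 10.2.3, for cord blood: "Women must have received a study drug regimen dose within 72 hours prior to delivery to be eligible for the cord blood sample collection".
- Protocol 3.1: "it is expected that some women will continue the study drug regimen postpartum". Section 5.1.1 describes Cohort 2 as third trimester and postpartum and sets the dosing interval at 7 days, give or take 2. Section 6.3 schedules a dosing visit in the first week after delivery.
- SAP, Infants: infant plasma and cord blood concentrations collected within 72 h of birth are summarised by count, range, mean, median and quartiles. The SAP has no stratum or flag for when the mother was dosed relative to birth.

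**The concern.** A sample that describes the infant at delivery should reflect drug carried over from dosing during pregnancy. The eligibility clock runs back from the draw, so part of the 72 h window can lie after birth. A maternal dose in that part makes the infant eligible, yet it can reach the infant only through breast milk. The last dose that could have crossed the placenta was a full dosing interval earlier.

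Such samples would be close to zero unless breast milk contributes materially. The protocol has no RPT breast-milk data and describes rifampicin levels in milk as very low. Pooled with infants whose qualifying dose preceded birth, they would pull the mean, median and quartiles reported for objective 2.2.5 downward. The reader could not tell, because the SAP does not separate them. With few infants eligible, a handful of such values can shift the quartiles.

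**Working it through.** The plan gives no figure on this point, so there is none to reproduce. The check has three parts.

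**1. What the rule admits.** Put birth at time 0 and the draw at age T hours, with T from 0 to 72 (10.2.4). The infant qualifies if the last maternal dose lies between T - 72 and T. The stretch from T - 72 to 0 is before birth; the stretch from 0 to T is after it. For any T above 0, a dose after delivery can qualify.

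The rule also errs the other way. With a dose 48 h before birth and a draw at 48 h of life, the dose is 96 h before the draw. The infant is not eligible, although the mother qualifies for cord blood.

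**2. What is left of the last in-utero dose.** If the qualifying dose came after birth, the previous dose was one interval earlier, so it was at least one interval before the draw. The half-life is 11-18 h (Protocol 1.2, non-pregnant adults; no neonatal value is given). Fraction left = 0.5^(hours / half-life).

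| Interval | Hours before draw, at least | Half-life 11 h | Half-life 18 h |
|---|---|---|---|
| 7 days | 168 | 0.003% | 0.155% |
| 5 days (shortest permitted) | 120 | 0.052% | 0.984% |

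At the draw, at most about 0.2% to 1% of peak remains. At birth more could remain. For a postpartum dose 0-72 h after birth, the previous dose was 168-96 h before birth at the 7-day interval, leaving 0.003% to 2.5%. At the 5-day interval it was 120-48 h before birth, leaving 0.05% to 16%. All these figures apply adult elimination to mother and newborn alike.

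**3. How many infants.** The documents give no share, so these are scenarios.

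- *Doses exactly on schedule.* Assume dose timing is uniform over the 168 h cycle relative to birth. The post-delivery share of eligible infants is T/72:
  - draw at 24 h: 24/72 = 33%
  - draw at 48 h: 48/72 = 67%
  - draws uniform over 0-24 h: 12/72 = 17%
  - draws uniform over 0-72 h: 36/72 = 50%

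  The formula reaches 100% at T = 72, which is a limiting case.
- *Doses due after birth given 2 days late, within the permitted window.* No such dose falls before 48 h, so the share is 0% for any draw by 48 h. For draws uniform over 0-72 h, the post-birth window averages (24 × 24 / 2) / 72 = 4 h and the pre-birth window averages 36 h. The share is 4 / (4 + 36) = 10%.
- *No dose between birth and draw.* 0%.

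For counts, 25 × 72/168 = 10.7 Cohort 2 infants would qualify if every mother were still on the regimen. A simulation with entry uniform over 28-34 weeks and delivery at 39.3 weeks (SD 1.5), both assumed, gives about 10 of 25. Its on-schedule shares are 33% at 24 h, 49% for uniform draws and 66% at 48 h. Of 10 eligible infants, that leaves about 6.7, 5.1 and 3.4 with a pre-delivery qualifying dose.

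**The case against.** The strongest reply is that the size is unknown and may be nil. A qualifying dose after birth has to be given under observation, after a provided meal, within three days of delivery. Doses may run 2 days late, and 12 doses may span 16 weeks (5.1.2). The infant draw is ideally done before the mother leaves hospital. This stands: the high shares hold only if every dose stays on its 7-day mark.

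The second reply is that a newborn sample after a postpartum dose is within scope. Outcome measure 9.2.2.2 reads only "RPT and desRPT concentrations in infants born to women receiving once-weekly RPT + INH", section 9.1 speaks of postpartum drug levels in infants, and section 8.1 recognises both in-utero and breast-milk exposure. This also stands in part. The mismatch is with objective 2.2.5 and with the cord-blood rule, and the samples are still worth having.

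A reader might infer three stronger things that the documents do not support:
- That an estimate of placental transfer, or a paired infant-to-cord comparison, is corrupted. The plan contains neither; the SAP lists descriptive statistics only.
- That a third to two-thirds of eligible infants are affected. That assumes exact scheduling through the first days postpartum, which no section states.
- That residual in-utero drug is always below 0.2% of peak. That fixes the interval at 7 days. The permitted 5 days gives about 1%, and the neonatal half-life is not given.

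None of this removes the point that the written rule admits such infants and the SAP does not identify them.

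**Conclusion.** The point holds as a mismatch of reference event. Sections 6.5 and 10.2.4 count back from the draw, while objective 2.2.5 and section 10.2.3 refer to delivery. An infant can therefore enter the summary on a dose it never received in utero, with at most about 0.2% (7-day interval) to 1% (5-day interval) of peak left from its last in-utero dose, at the adult half-life. The effect on the summary is downward relative to infants whose qualifying dose preceded birth, provided that little drug arrives through breast milk. The share affected runs from 0% to about two-thirds across the scenarios and is about 10% under a plausible 2-day delay; the documents do not fix it. The wording is certain and the impact is not. The objective is secondary and descriptive, so no sample size, power or alpha is affected.

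**What to change.** **Protocol.** Reconcile the reference event in 6.5 and 10.2.4 with objective 2.2.5 and with 10.2.3. If the infant rule were tied to delivery as the cord rule is, about the same number would qualify under the assumptions above (72 h out of each 168 h cycle either way). A draw could then be up to 72 + 72 = 144 h after the dose, so time since dose would have to be reported.

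**SAP.** Use the dose, birth and draw times to report infant concentrations by time from the last pre-delivery dose. List separately, outside the at-delivery summary, any infant whose mother was dosed between birth and the draw, as possible breast-milk exposure. This also covers samples already taken under the present rule.

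**Cost.** No new visits, samples or assays. Doses are directly observed and the SAP already checks sampling times relative to dosing; birth time must be carried into the dataset if it is not there. The downside is a smaller at-delivery summary: about 5-7 of 10 eligible infants if doses stay on schedule, and about 3-4 if draws also cluster at 48 h.
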